## Recruitment of PSI health care workers

PSI health care workers who provide outreach services in the study communities will be purposively selected to ensure representation of teams from all five provinces. Eligibility criteria for PSI health care workers:

- Having provided outreach services in the study communities during the study period
- Willing and able to provide written informed consent for study participation

#### Recruitment of CBDs

CBDs will be recruited from the eight process evaluation study communities. Purposive selection will be done to ensure inclusion of both low and high 'performing' CBDs (based on number of clients in respective catchment area who take up services at PSI outreach sites. Inclusion criteria for CBDs:

- Working as a CBD in any of the 8 communities mentioned above
- Willing and able to provide written informed consent for participation

## Recruitment of public sector health care workers

Public sector health care workers who provide ART services in 8 communities mentioned above will be recruited. Purposive sampling will be done to ensure representation of all cadres who provide HIV services in the 8 communities. Eligibility criteria:

- Providing HIV services at health facilities
- Willing and able to provide written informed consent

The in-depth interviews described above will be conducted by trained study staff according to an interview guide. They will be audio-recorded, transcribed and analysed according to thematic analysis.

## 4.2.6 Population-based Survey

A representative population-based survey will be conducted six weeks after the first PSI outreach visit in four randomly-selected enumeration areas (EAs) in each study community. Two survey teams of eight people will each survey one community per week. It is anticipated that we will recruit 50 people per EA, giving an anticipated total of 200 surveyed adults in each community.

Survey questionnaires will be self-administered using Audio Computer Assisted Self Interview (ACASI) on computer tablets, and will be piloted. Respondents will be asked whether they or other household members were offered, accepted, used self-test kits and if not why not; their experience of self-testing, whether they chose to link to services, what factors influenced their decision to attend or not attend, what their experience was, whether they would opt to self-test again, recommend to a friend etc. In addition, information on previous testing history and ART experience of household members will be collected.

Furthermore, survey participants will be asked to give a finger-prick blood sample that is collected on dried blood spot filter paper according to standards set by the United States National Committee for Clinical Laboratory Standards (NCCLS) published in "Blood Collection on Filter Paper for Neonatal Screening Programs" (LA4-A; 1997). The samples will be air dried onto filter paper and stored at room temperature until they are transported to PSI Zimbabwe's laboratory in Harare for HIV-1 antibody testing using validated testing algorithms. The filter papers will be labeled with unique barcodes that are also entered into the tablet for the corresponding questionnaires to ensure that survey data can be linked to laboratory results. Identifying information will be collected on the consent form, which will not be linked with survey materials. DBS samples will be stored at -20°C and then tested in batches. They will be tested serially for HIV-1 antibody with discrepant results resolved by PCR. Testing for viral load will be carried out on all samples which are HIV antibody positive on DBS (as well as a sub-set of those HIV antibody negative) using the Abbot Real Time HIV-1 m2000 viral load assay. All samples that are confirmed HIV infected will be tested using a qualitative assay for the following antiretroviral drugs Efavirenz, Nevirapine, Lopinavir and Atazanavir. Samples that are confirmed HIV positive will also be tested for recency of HIV infection using the lag avidity assay. The tests will be conducted at local laboratories in Zimbabwe. In the event that it is not possible to get local tests for drug levels and recency of infection, samples will be shipped for testing at a South African laboratory. Participants will be asked to consent for specimen shipment.

After administering the questionnaire, participants will be strongly encouraged to get tested and know their HIV status if they did not test recently. In addition, they will be given the option to obtain their DBS HIV and viral load results (if applicable) at their local clinic. While minimum identifying data is collected during informed consent, if participants wish to receive their results they will be requested to provide additional identifying information (i.e., name, date of birth, national ID number, address), which will be linked with their blood samples using a numerical barcode label. However, if participants explicitly say that they do not want to receive their HIV test results, no additional identifying information will be collected and their HIV test results will not be sent to the local clinic. HIV test results will be available within two months of the survey date (to allow for specimen testing and transportation to and from the laboratory). The clinics will be asked to keep the HIV test results for 3 months, so participants are able to pick up their results in 2 to 5 months of the survey date. Participants will be able to collect their HIV test results at the local health facility with their national ID card (or some other form of identification if National ID card is not available), to allow identity verification. HIV test results will be sent to the clinics in sealed envelopes; nurses will only know the HIV test results of the participants that go to the clinic to receive their results.

## Inclusion criteria for survey participants

- At least 16 years of age
- Willing and able to provide written informed consent
- Have resided in the community for the last three months

## 4.2.7 Refining procedures for facilitating linkage to care

## Discrete choice experiments

Discrete choice experiments will be conducted in study communities to determine client preferences for methods of facilitating linkage to prevention and care services. Because DCEs are typically used to test preferences of programme packages, the preference of other programme attributes that might stimulate linkage to prevention and care services as revealed in formative qualitative research will also be tested.

## **Developing the DCE questionnaire**

DCEs will be kept simple by investigating a small number of attributes. Hypothetical alternatives for each attribute will be developed and these will be combined into choice sets, which the questionnaire will be based on. An example of a choice set that might be given is shown in Fig 4 below. The computer programme NGENE will generate a series of choice sets to capture optimal variation in attribute levels across the choices, allowing for the most efficient design of the experiment (called a d-efficient design). As such we will be able to retrieve the most information from each choice without overburdening respondents with excessive numbers of repeated scenarios. Participants will be presented with a number of choice pairs (between 8 and 12) and will be asked to make a choice on which set of conditions might best motivate uptake of post-test prevention and care services. An opt-out choice will allow for respondents to state if neither of the linkages would induce them to seek follow-up care. In addition, for respondents who choose neither option, there will be a second question where participants will be constrained to take account of their own circumstances and indicate whether they would choose the first or second option. The questionnaire will be completed on paper and will be piloted before use.

Attribute	Attribute level								
	Programme 1	ramme 1 Programme 2 Not s							
Method of disbursing	Airtime	(Opt-Out)							
incentives for linkage									
Form of referral	SMS referral	Referral letter							
letter									
Volume of people at	Very quiet site, few								
outreach testing site	people at a time								
Attitude of health	Friendly staff	Friendly staff							
care centre staff									
User fees	No fees levied	No fees levied	No Fees						
CHOICE									

Fig 3: An example of a choice set that might be developed

## **Recruitment and Sample sizes for the DCE**

The first 500 participants who complete the household survey will also be asked to complete the DCE. As stated for the distribution DCE above this number is based on pragmatic considerations and is within the range of other DCE studies in the literature [25, 26].

## Data analysis for the DCE

Discrete Choice models will be used to estimate changes in the odds of linkage to prevention and treatment services associated with changes in attribute levels moving from one alternative to another. We will also look at preferences by user / client characteristics and how much variation in preferences there are.

## 4.2.8 HIV Self-Testing costing study

The costing study will adopt the provider's perspective: detailed costing of all resources used in the provision of HIV self-testing services and in the support of linkage to HIV care and VMMC will be done.

Cost data will be collated from project accounts as well as time and motion studies. An ingredients based approach will be used to collect costs based on actual expenses for capital items, and recurrent costs. University College London researchers will conduct cost effectiveness analysis and economic modelling using the cost data from Zimbabwe. An inter-country protocol will be written for this work.

## 4.2.9 Process evaluation

The process evaluation will be used to provide information on how and why interventions resulted in improved linkage to prevention and care services (or why there was no observed effect). Throughout the study, data will be collected to capture progress and adherence to programme activities and timelines.

Inputs — Process — Outputs — Impact -> Outcomes -**Provision of** Financial. Coverage, Improved **Reduction in** human & activities health seeking quality **HIV Self-test** organisational & services & behaviour kit prices (testing and linkage resources acceptability

The process evaluation framework below provides a structure for measuring the progress.

For the process evaluation, we hypothesise that:

- If there are adequate project inputs (financial and human resources, partnerships and collaboration, established procedures and protocols, effective trainings),
- these will ensure a smooth process of implementation,
- producing well-functioning outputs (efficient and high quality clinic services, motivated and skilled staff, community uptake of HIV self-testing.
- Subsequently, if the intervention outputs have good coverage, are feasible to deliver, and considered acceptable to the communities,
- they will contribute to outcomes necessary for achieving the intervention's ultimate goals
  or impact including improved uptake of HIV testing, including repeat testing and linkage
  to prevention and care services. By demonstrating the feasibility and acceptability of selftesting, plus the potential cost effectiveness it is anticipated this will ultimately result in
  an increase in the market for HIV self-test kits with a commensurate reduction in prices.

The intervention impacts will be assessed through overall analysis across all participating countries. The outcomes related to uptake of HIV testing and linkage to prevention and care will be measured in the trial, and are thus not included in the monitoring and process evaluation framework, which documents only the lower stages of the pathway. Although data collected through the framework cannot prove causal relationships between stages, they can build up a more comprehensive picture of what "actually happened" during implementation

and how this may have affected observed outcomes. The research questions for each level of the framework are as follows:

(1)	Inputs: How ma	any resources were required to deliver the intervention?
		Were these adequate given the activities implemented?
		Were resources well managed and appropriately allocated?
(2)	Process:	Did activities occur according to the intervention design?
		Were all intervention components delivered?
		How did timing of implementation compare to plans?
(3)	Outputs:	What was the coverage of each intervention activity?
		Was implementation of the activities feasible (from the perspective of programme) and acceptable (from the perspective of clients/community)? At what intensity was the intervention delivered (frequency of contact, number of different activities length of quents)?
		What were the levels of quality achieved (assessed by external criteria according to standards set by the intervention, as well as from the perspectives of clients/community)?
(4)	Outcomes:	Have programmatic messages been adopted? Are behaviours that are known determinants of expected impacts being taken up?

Is there evidence of changing environmental factors?

Implementati	on of Intervention	Coverage & Intensity
Inputs/ Preparation •Partnership with relevant partner agencies established (MoH, xxx) •New staff (including community based distributors) recruited, trained and deployed •PSI procedures and sites set-up for self-testing roll-out •Referral mechanisms put into place, including training of public sector health care workers •Community mobilisation activity protocols and tools introduced	Activities KIT DISTRIBUTION •Community education on programme and important dates •Kit distribution LINKAGE TO CARE •PSI outreach visits at each of the time points as per protocol • Distribution of incentives to both CBDs and clients for linkage, and to health care workers for linkage notification •Training public health care workers on communication of referral uptake by SMS	Programme Delivery         •Number of community mobilisation/education meetings held         •Number of community mobilisation/education meetings held         •Number of this distributed         •Number of CBDs, health care workers and clients receiving incentives         Quality of Activities         •Proportion of general population who have received ST kits         •Timing of outreach visits (adherence to schedule)         •Proportion of CBDs, clients and HCW receiving their incentives on time         •All well woman/well man services provided as per protocol; all supplies in stock         •Knowledge & awareness of importance of testing & linkage to prevention and care services increased         Acceptability of Interventions         PSI Staff (including CBDs) and public sector health care worker perceptions         •Positive & negative experiences         •Programme strengths & weaknesses         Client perceptions         •Positive & negative experiences         •Likes & dislikes in delivery of services
	Т	ools
Checklist of planned activities, with dates     Staff records: % of staff hired and still in place each year;     Trainings:# conducted and % staff attending     Programme records: # community mobilisation activities designed; # sensitisation/training meetings planned with public institution health care workers	
 
Programme records: # of community education/mobilisation /outreach visits actually done
 
Number and timing of kit distribution
 
Distribution of incentives
 
	
 
Surveys: % received ST kits; knowledge and awareness of importance of testing and linkage to care
 
Qualitative studies (in-depth interviews and FGDs) - PSI staff, public sector health care workers and client perspectives
 
Programme records: number and frequency of outreach visits and adherence to schedule, adherence to schedules for giving client, CBD and public health care worker incentives; inventory records for critical supplies like ST kits and other products required for well woman/man clinics
 

Monitoring and process evaluation data collection

## Checklists

A prospective record should be maintained of if/when planned activities (as per protocol) were implemented.

## Staff and training records

Routine programme documentation on start-up activities of the project, including the number of staff hired and deployed, and how many attended all relevant trainings. These will be reviewed annually and at the end of the project if staff retention/performance is considered to be an issue affecting the delivery of intervention components.

## CBD kit delivery and support documents

CBDs will be given forms on which to record all contact with households in their catchment area. These will be used to document the number of kits delivered per household, date of delivery, any help that clients may have asked for and the timing of this.

## Programme Records

Staff facilitating community mobilisation meetings will fill out forms to capture the following:

- (1) Location, duration & topics covered at each organised meeting/event
- (2) Number of health care workers, CBDs or clients attending the meeting/event

Programme records will also be maintained to ensure that the following data will be obtained about outreach visits and linkage to HIV prevention and care services:

- Dates and location of outreach visits to each community
- Uptake of various well-woman and well-man services at each outreach visit
- Log of uptake of various outreach services, by CBD
- Schedule of payment to CBDs
- Number of HIV positive clients initiated on ART and referred to public health care institutions
- Log of SMS attendance confirmation that has been sent in by health care workers
- Schedule of payment of health care workers for referral notification
- Schedule of payment of transport reimbursement for those clients who took up referral
- Stock cards for the various supplies and commodities that are necessary for the provision of well-man and well-woman services

#### SURVEYS

Surveys will be conducted as part of the research. Some research outcomes in the survey will also be used as process outcomes, e.g. the proportion of individuals who received HIV self-test kits and knowledge of the importance of HIV testing and linkage to prevention and care services.

#### QUALITATIVE DATA

Qualitative studies will be done soon after the start of program implementation, and at the end of each 12-month period.

#### Site selection for the qualitative studies

Eight study communities (wards, two in each arm of the study) will be purposively selected for the process evaluation. PSI program data for the first month will be used to inform site selection in order to ensure representation of both areas with good and poorer uptake of 'well-woman' and 'well man' services.

#### Qualitative studies

The in-depth interviews described in section 4.2.5 will also be used for process evaluation.

In-depth interviews will be conducted with CBDs to explore their views on the ST program. They will be asked about what is going well, what is going less well and recommendations for change. Purposive

sampling will be done to ensure inclusion of CBDs in all trial arms, and to include those associated with both good and poor uptake of outreach services after self-testing.

Interviews and FGDs will also be held with clients in all arms of the study. Clients will be asked about their view of the program and procedures for kit distribution, views about having the CBDs come into their homes, whether they feel able to seek help from CBDs, barriers and facilitators to self-testing and linkage to care, and views on incentives for linkage. Purposive sampling will be done to ensure inclusion of clients in all study arms, those who linked or did not link to outreach visits, and those who linked or did not link to HIV care and treatment services at public health care institutions. Focus group discussions will be particularly used to explore views on how communities can take a leading role on distribution models. 16 FGDs will be conducted in total: 8 (four among males) among individuals who live in Mazowe communities where HIV self-tests were distributed, and 8 (four among males) among individuals who live in Mazowe communities where *no* distribution of kits occurred. Mazowe district has been selected for FGDs for pragmatic reasons as it the closest study district to Harare, where the study team is based.

Interviews will also be done with PSI and public sector health care workers to explore their views on the programme, what is working well and what is not, and recommendations for improvement. All indepth interviews and FGDs will be audio-recorded, transcribed and analysed according to thematic analysis.

## Audio diaries

Before the beginning of each implementation cycle, purposively selected CBDs in the 8 study communities will be given audio recorders where they will be asked to audio record their experiences of distribution of self-test kits and perceptions of the intervention. They will be given a written guide on what sort of experiences and impressions they are expected to record, and examples of when it might be useful to do this, e.g. in the evening after a day of kit distribution or mobilisation for uptake of 'well woman' and 'well man' activities. The audio diaries will be collected from the CBDs six weeks after kit distribution.

Audio-diaries will be transcribed verbatim, translated, and analysed according to thematic analysis.

## **Project diary**

A calendar or diary will be kept by a member of the research team to record any events (particularly external) that may affect ability of the intervention to be delivered as planned. Political events, local festivities, or other health promotion campaigns should be noted, with a description of their activities and effect. Internal events that have bearing on implementation (such as increased funding, or breakdown of a project vehicle) will also be noted to help contextualise other information collected.

## 4.3 Pilot HIVST kit distribution at New Start HIV testing Centres

Distribution will occur in six geographic areas where New Start HIV testing services are offered in the following cities: Harare, Bulawayo, Chitungwiza, Masvingo, Mutare and Gweru. Three channels of

HIVST distribution will be employed: 1) distribution at static sites through the offer of a choice between PDHTC or HIVST; 2) distribution to partners of individuals who test HIV positive at the static sites, and 3) distribution during testing and counselling outreach in urban areas in Bulawayo and Harare. In this model we aim to:

- 1. Determine the acceptability of HIVST among individuals who seek HTS within New Start static and mobile sites in urban areas
- 2. Determine HIV yield among clients who are given HIV self-test kits compared to those who opt to test using PDHTC
- 3. Measure uptake of self-test kits for partners among clients who have tested HIV positive at New Start Static sites
- 4. Determine rates of linkage to HIV care, voluntary medical male circumcision (VMMC), and PrEP (offered to women aged 18-24) among individuals who are given HIV-self-test kits
- 5. Determine the cost and cost-effectiveness of providing HIVST through New Start HIV testing services

Detailed procedures are given in Appendix 1, Standard Operating Procedures (SOP) for the New Start Model.

Late read of returned used self-test kits will be done as detailed in the SOP. In addition, a visual stability study of used test kits will be done at New Africa House New Start Centre. Participants who give verbal consent for their used test kits to be anonymously used in the study will place their used test kit in a separate drop box that is earmarked for this purpose. This drop box will be emptied every ten minutes for immediate late read of results (as opposed to the regular drop box which will be emptied on a weekly basis. The visual stability study procedures are detailed in Appendix 1a. In brief, all test kits collected for the visual stability study will be re-read at regular intervals, under ambient conditions in the PSI laboratory, for a period of 12 months.

340 participants will be recruited for the visual stability study. This sample size is justified as follows: based on a previous study by Choko *et al.* [27] the rate of change over a one year period for HIVST (Ora Quick) was 0.2%. Assuming there will be no difference in the proportion changing result, a sample size of 307 kits will provide precision of +/- 0.5% at the 95% confidence interval level. Therefore, we will collect at least 340 kits (this factors in a 10% loss).

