## 4.2.3 Distribution of self-test kits and PSI programme activities

HIV self-test kits will be distributed by CBDs to all households in the study communities. CBDs will ensure that each household receives a kit for each member of the household who is willing to test. At time of kit distribution, CBDs will give out appointment cards on which clients will document the intended date and time of performing the self-test. This will ensure that clients make a commitment to self-test (an intervention that previous research has proven effective in ensuring future uptake of health interventions [23, 24]). CBDs will inform clients of the date of the next PSI outreach visit, and encourage them to think about the time that they would like to attend the outreach clinic. The client will be asked to write this time on their card, which will help foster a commitment to attend post-test services. The card will have the CBD identity number, and clients will be asked to take it to the outreach clinic.

Once they have self-tested, clients/participants will be asked to complete a short results form and to return both the form and the used test kit in a sealed envelope to a drop-off point in the community. The used kits will be placed in locked boxes that will be kept at health facilities. In addition, CBDs will also keep locked drop-boxes where clients can deposit their used test kits. No client identifiers will be placed on the used test kits, although it will be possible to know which household the kit came from. On a weekly basis PSI will collect the sealed boxes. Only authorised PSI staff will have the keys to the drop boxes. A late read of results of the returned kits will be done to estimate HIV prevalence among the HIV self-testers.

One to two weeks after self-test kits have been distributed to households within a community, a PSI outreach team will visit the community to provide a comprehensive package of services packaged as 'well woman' and 'well man' services. These services will include client-initiated counselling and

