## Analysis of Results

An interim analysis of the results will be reviewed at six months. All the recorded visual reads for each individual test result will be analysed for any change in the visualised test line. This will include a non-reactive test result changing to a reactive test result, an initial reactive test result changing to a non-reactive test result, an initial invalid test result changing to valid test result, an initial valid test result changing to an invalid test result. The intensities of the recorded lines will also be analysed for any

changes- strong to weak, weak to strong, weak to non-reactive etc. Any changes in the test devices will then be analysed against the daily recorded temperatures and humidity to look for any correlations.

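### The visual stability study's stated precision of ±0.5% from 307 kits rests on a normal approximation with about 0.6 expected events; exact 95% half-widths are about 0.6 to 0.9 points for the likely results

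*Protocol*

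**What the plan says.** Protocol section 4.3 gives the whole sample-size justification for the visual stability study in a few sentences. It takes from a previous study that "the rate of change over a one year period for HIVST (Ora Quick) was 0.2"%, and concludes that "a sample size of 307 kits will provide precision of +/- 0.5% at the 95% confidence interval level". It then allows for loss: "we will collect at least 340 kits (this factors in a 10% loss"). The recruitment target follows: "340 participants will be recruited for the visual stability study". The kits are to be "re-read at regular intervals, under ambient conditions in the PSI laboratory, for a period of 12 months".

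Section 4.3 does not name the interval method behind the ±0.5%. Appendix 1a (Analysis of Results) lists the kinds of change to be examined, among them "an initial reactive test result changing to a non-reactive test result", and does not name an interval method either.

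**The concern.** The expected proportion, 0.2%, is smaller than the stated margin, 0.5 points. A symmetric interval of that width around that value must cross zero, which is the usual sign that a normal approximation has been used for a rare event. With some 300 kits, fewer than one changed kit is expected, so the result will probably be none or one, and the interval should be judged at those counts.

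What is at stake is the stated reason for choosing 307 kits. The protocol presents ±0.5% as something the design will provide. If the design cannot provide it, someone relying on section 4.3 would expect the study to exclude change rates above about 0.7%, when the likely results leave rates up to 1.2% or 1.8% open.

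**Working it through.** **Inputs (all from Protocol section 4.3).** Change rate p = 0.002; margin d = 0.005; confidence 95%, taken as two-sided (z = 1.96); evaluable kits n = 307; collected 340 with 10% loss.

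**1. The plan's own figure.** n = z² p(1 − p) / d² = 1.96² × 0.002 × 0.998 / 0.005² = 306.7, rounded up to 307. The half-width at n = 307 is 1.96 × √(0.002 × 0.998 / 307) = 0.4998 points. So 307 reproduces, and the method can be inferred to be Wald. For loss, 307/0.9 rounds up to 342 and 307 × 1.1 rounds up to 338; the stated 340 lies between them and raises no issue.

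**2. Is the approximation valid here?**
- Expected changed kits: 307 × 0.002 = 0.614 (340 × 0.002 = 0.68).
- Implied interval: 0.2% ± 0.5 points = -0.3% to 0.7%. The lower limit is impossible.
- Probabilities at p = 0.002, n = 307: no changes 0.998^307 = 54%; one 33%; two 10%. No or one change: 0.541 + 0.333 = 87%.
- The Wald half-width at the counts that can occur is 0 points for no changes, 0.64 for one and 0.90 for two. The planned 0.50 belongs to 0.614 changed kits, which cannot be observed.
- With no changes the Wald interval has zero width and misses 0.2%. That alone removes 54% of the coverage; actual coverage is about 46%, against a nominal 95%.

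**3. Exact (Clopper-Pearson) two-sided 95% intervals.** For no changes the upper limit is 1 − 0.025^(1/n). For x changes the limits are the 2.5% quantile of Beta(x, n − x + 1) and the 97.5% quantile of Beta(x + 1, n − x).

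| Kits | Changes | Probability at 0.2% | Exact 95% interval | Half-width (points) |
|---|---|---|---|---|
| 307 | 0 | 54% | 0 to 1.19% | 0.60 |
| 307 | 1 | 33% | 0.01% to 1.80% | 0.90 |
| 307 | 2 | 10% | 0.08% to 2.33% | 1.13 |
| 340 | 0 | 51% | 0 to 1.08% | 0.54 |

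Wilson intervals give nearly the same upper limits at 307 kits: 1.24% for no changes and 1.82% for one.

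**4. Like-for-like comparison.** Half-width against half-width, the likely results give 0.60 or 0.90 points against the stated 0.5. Upper limit against upper limit, they give 1.19% or 1.80% against the implied 0.7%.

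**5. What ±0.5 would take.** Evaluated at the expected count, an exact half-width of 0.5 points needs about 580 kits. For the exact upper limit to lie within 0.5 points of an estimate near 0.2%, about 1,040 to 1,055 kits are needed.

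**The case against.** The strongest defence is that 307 is calculated correctly and serves only as a planning figure for a small laboratory sub-study. Several parts of that defence stand.

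- **Not an arithmetic error.** The formula is evaluated correctly; the fault is applying it where it does not hold.
- **The shortfall is modest on a common scale.** A reader might set 1.2% to 1.8% against ±0.5% and infer that the plan is wrong by a factor of two to three. That compares upper limits with a half-width. The like-for-like excess is 0.1 points for no changes and 0.4 points for one.
- **The point estimate is likely to be close.** It falls within 0.5 points of a true 0.2% with probability about 98%. But section 4.3 makes its claim about the confidence interval, so this does not rescue it.
- **Convention for no changes.** A one-sided 95% bound at 307 kits is 0.97%, and half of that is just under 0.5. This helps only when no kit changes, and the limit is still 0.97 points above the estimate.

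Three stronger readings are tempting, but the documents do not support them.

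- **Prevalence.** Section 4.2.3 says "A late read of results of the returned kits will be done to estimate HIV prevalence among the HIV self-testers", so a reader might infer that the one-year change rate underpins that estimate. Nothing in the protocol says that it will be used to support or correct it. Those kits are collected weekly from community drop-boxes, whereas this study follows on-site kits from one centre for 12 months.
- **Pooled directions of change.** A reader might infer that the plan mixes false-reactive and false-non-reactive changes. Appendix 1a already lists them separately, and section 4.3 does not say how the previous study defined its 0.2%. Any precision figure for reactive kits alone would need a positivity that the documents do not give for these clients.
- **Misreporting.** The interval method for the results is commonly left to a statistical analysis plan, which is not at hand. Its absence is no finding, and nothing shows that the result would be reported as known to ±0.5%.

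**Conclusion.** The precision statement in section 4.3 is wrong as written. With two-sided 95% exact intervals, no result from 307 kits, nor from all 340, reaches a half-width of 0.5 points: the narrowest case at each size is no changes, which gives 0.60 and 0.54. At 307 kits the second likeliest result gives 0.90.

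This rests on the protocol's own 0.2% rate, on reading its 95% as two-sided, and on inferring the Wald formula from the match to 307. The conclusion about exact half-widths does not depend on that inference. The probabilities (54%, 33%, 87%) and the 46% coverage do depend on the true rate being 0.2%.

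The consequence is limited to how the visual stability study describes its precision. The cluster-randomised trial's primary outcome, power and analysis are unaffected.

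**What to change.** Keep 307 evaluable and 340 collected kits. In section 4.3, replace the ±0.5% statement with exact limits, for example: *With 307 evaluable kits, an exact (Clopper-Pearson) 95% interval has an upper limit of 1.2% if no kit changes result and 1.8% if one does.* Use exact intervals when the change rate is reported.

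The cost is a change of wording and a less favourable stated precision; no procedure changes. If the sponsor does need a half-width of 0.5 points, that is a different and larger study (about 580 kits on the basis shown in the working), and the choice should be made explicitly.
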